**Project Title:** Hearing Impairment, Strategies and Outcomes in VA Emergency Departments

**Principal Investigator:** [name], MSHS

**Site:** 630 – New York Harbor Healthcare System

Study Goals:

- 1) Establish the feasibility of screening for hearing loss in the ED
- 2) Determine the acceptability of the screening procedure (among ED population)
- 3) Derive a preliminary estimate of effect size of primary outcomes
- 4) Identify the evidence that decision makers in VAMCs, ED and Audiology Services need to commit to this approach

Study Outline:

- 18 month funding period, to include: four month start-up, 12 months of intervention, and two months of analysis, disseminations, and plans for next steps to advance hearing healthcare in VA health system
- Minimum goal of 68 and maximum is 150 (across both Manhattan and Brooklyn)
- Patients will be randomized to receiving a HAD or control
- Data collections from VA CPS, RA observations, 10-minute RA survey, and brief qualitative follow-up interviews with patients, nurses, physicians. Follow-up calls three-days and 30-day ED visits will occur.
- Brief semi-structured interviews with 10 veterans willing to speak more extensively after discharge from ED
- Brief semi-structured interviews with 10 nurses and physicians (providers) will assess their experiences with the hearing-impaired patients

Milestones/Developmental Progress Goals (DPGs):

We will track and report on these Milestones regardless of your decision about the feasibility of continued support beyond the 18-month period.

- Hiring and training of research staff
- Successful recruitment of at least 68 subjects who consent to hearing screening in the Emergency Department
- Completion of the HHIE for 85% of consented patients
- Delivery and fitting of the PockeTalker™ for 85% of patients who score > 10 on the HHIE
- Completion of the HAD use survey for 70% of patients who are given PockeTalkers™
- Completion of the 6-item measure of quality of hearing, understanding, and communication for 70%
- Completion of the CTM-3 for these same 70%
- Successful pilot test of the Patient Understanding of Discharge Instructions (PUDI) for 10 subjects
- Completed semi-structured interviews these 10 subjects and research staff to assess feasibility and refine processes
- Completion of three virtual advisory council meetings with 70% attendance
- Preparation of a summary report of these virtual meetings addressing key issues of feasibility/implementation

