completion, 68 Veterans per year will complete this study. These highly conservative estimates ensure that we will achieve our desired minimum sample size of 180 Veterans if we continue the study beyond one year of recruitment. Our minimum goal for 12 months is 68 Veterans and maximum goal is 120.

We used simulation methods to estimate power and sample size requirements. We generated data from literature-based assumptions in each iteration for a specific sample size and an assumed effect size for each outcome. For each iteration, we conducted two t-tests in accordance with the multiple testing corrections and recorded whether one or both null hypotheses were rejected. For each sample size/effect size combination, we ran 1500 iterations; we calculated power as the proportion of iterations in which both null hypotheses were rejected. We evaluated total study (both arms) sample sizes ranging from 70 to 150.

We used simulation methods to estimate power and sample size requirements. We generated data from literature-based assumptions in each iteration for a specific sample size and an assumed effect size for each outcome. For each iteration, we conducted two t-tests in accordance with the multiple testing corrections and recorded whether one or both null hypotheses were rejected. Note that sample size estimates will only be relevant should be given approval to continue for the four-year duration of the Merit. Given the nature of this "developmental" Merit, continuation beyond 18 months is contingent on our findings at that time.

Specific description of how data will be collected

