proper function. These subjects will be encouraged to use the HAD during any encounters with ED staff and others (for example, family). All consenting subjects will understand that consent includes: (1) completion of a post ED-care 10- minute survey and brief telephone follow-up four days after discharge, (2) abstraction of their medical records, and (3) awareness of the risks and benefits of participation. All consenting subjects will receive \$20 cash and be able to keep the HAD when leaving the ED if they have found it to be helpful. If randomization is successful, the two groups should vary only in receipt of the HAD, which we hypothesize will affect downstream outcomes.

Plan for and specification of the purpose of any interim analysis of the data

Before addressing the specific aims, the data will be summarized numerically using descriptive statistics. Comparison of the baseline characteristics between the two treatment groups will be performed using chi-square tests for categorical data and t-tests or nonparametric tests for ordinal or continuous data.

We will compare intervention and control subjects with respect to baseline sociodemographic characteristics (age, gender, race, and education), comorbid medical conditions, and the Charlson comorbidity index and other potential co-variable measures. We will assess whether any adjustments need to be made in the final statistical models if we determine the differences are clinically meaningful. Besides the primary analyses described below, we will conduct exploratory mediation analyses with the goal of developing a better understanding of the mechanisms of the intervention. We will use R 3.3.2 (R Foundation for Statistical Computing, Vienna, Austria) for all analyses.

Methods for handling missing data points and subject dropouts

Missing data: We anticipate less than 5% loss to follow-up, as a majority of data is collected during one ED visit. If missingness is higher, multiple imputation will be used to estimate the group differences and the uncertainty due to missingness, under the assumption of missingness at random (MAR).

Definitions of Covariates

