With regard to semi-structured interviews with staff (nurses and physicians), all staff will be informed about the study procedures in terms of 1) knowing that this is a study about hearing impairment; 2) that we are interested in understanding the utility of using HADs during an ED visit and that we will match staff characteristics (gender and spoken language) with each patient that is an enrolled subject. Staff will also know that a research assistant may approach them for a brief conversation about their experience with specific patients and about HAD use, in general. They will understand that they are free to participate or refuse participation and their decision will not be known to their supervisor and will not impact their employment in any way. They will be asked permission for the RA to audio record their conversation and they will know that as soon as that conversation is transcribed (and without identifiers), that tape recording will be erased. They will also know that we will attempt to survey all nurses and physicians at least once who are working during those times that patients are participating in HearVA-ED.

Methods for Dealing with Data Transformations

Missing – Missing data will be removed by multiple imputation or by being re-coded into a “missing” category.

Distribution of Data – The distribution of the data will be determined. Non-normally distributed data will be transformed using log transformation.

Definitions of Analytical Sets

Intent-to-treat – Analysis will be conducted with patients included in their randomly assigned group (opt in versus opt out), regardless of the treatment received.

Complete-case – Analysis conducted including only participants who have no incomplete data regarding their treatment.

Adverse and Serious Adverse Events

Standard IRB-approved and HIPAA compliant measures will be used to maintain Veteran confidentiality, privacy, and data security that adhere to the standards of the VA privacy officer, Information Security Officer, and Chief Information Officer. All study personnel have already taken or will take the mandatory VA HIPAA training to ensure that they are aware of the importance of Veteran confidentiality and all appropriate laws regarding the protection against Veteran privacy breaches. Procedures will be in place to ensure that all files containing Veteran information will be kept in VA-encrypted, locked databases on VA computers. There will also be

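### The SAP's blanket log-transformation rule lets the observed distribution decide whether a scored outcome's effect is a difference in points or a ratio; the harm is minor and the repair is a few sentences

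*SAP*

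**What the plan says.** The SAP's whole treatment of distributional shape is two sentences under Methods for Dealing with Data Transformations: "The distribution of the data will be determined", and then "Non-normally distributed data will be transformed using log transformation". The second is an instruction, not an option. It names no variables, normality criterion, direction of skew, offset for zeros, fallback or back-transformation.

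Three other places might have limited it for outcomes, and none does:

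- The section headed as the interim-analysis plan allows "chi-square tests for categorical data and t-tests or nonparametric tests for ordinal or continuous data", but for comparing the arms at baseline.
- The same section says "Besides the primary analyses described below, we will conduct exploratory mediation analyses". No outcome model or estimator follows.
- Rationale for the study sample size says "For each iteration, we conducted two t-tests in accordance with the multiple testing corrections". That describes the power simulation, not the analysis of the trial.

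The Protocol's Study Goals include "Derive a preliminary estimate of effect size of primary outcomes", with no scale given. The documents do not label the primary outcomes. The 6-item hearing and communication measure and the CTM-3, both in the Protocol's milestones, are presumed here to be scored outcomes; their score ranges are not given.

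**The concern.** An untransformed comparison of means estimates a difference in points. The same comparison on logs, back-transformed, estimates a ratio of geometric means. These are different quantities, and the rule lets the collected data choose between them by a criterion nobody has written down. Two analysts who both followed the SAP could report different effect measures for the same outcome, or one outcome could be logged and another not.

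There are two further difficulties. A log pulls in the upper tail and stretches the lower one, so it suits right skew and aggravates left skew, which is what satisfaction-type scores would show if they cluster near the top. And the log of zero does not exist, while several baseline variables can be zero.

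What is at stake is the interpretability of the effect estimate that Goal 3 is meant to supply, and its comparability with the t-tests behind the power work.

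**Working it through.** **Sample size used.** The SAP's funnel reproduces: 230 × 0.70 = 161 (stated as 160); 160 × 0.50 = 80; 80 × 0.95 = 76; 76 × 0.90 = 68.4, so 68 completers. Allocation is not stated; 1:1 is assumed, giving 68 / 2 = 34 per arm. The SAP's power cannot be reproduced, because no alpha, effect size, SD or power value is reported.

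**Two estimands.** Raw scale: mean₁ − mean₀. Log scale: exp(mean log₁ − mean log₀), a ratio of geometric means. Converting a ratio to points needs the control level. A ratio of 1.10 is about 2.5 × 0.10 = 0.25 points from a control level of 2.5, and 4.5 × 0.10 = 0.45 points from 4.5.

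**How often the rule fires.** This depends on shape, sample size and the missing criterion. All shapes are assumed.

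- Mildly left-skewed score (100 × Beta(4,2) against 100 × Beta(5.5,2)), Shapiro-Wilk at 0.05 on within-arm residuals: 51% of trials at N = 68, 85% at 120, 94% at 150.
- Symmetric three-item score at N = 68: 40% (Shapiro-Wilk on residuals), 64% (Shapiro-Wilk in either arm), 5% (|skew| > 0.5), 0% (|skew| > 1).
- Scores assumed to cluster at the ceiling: 81% to 100%.

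**Left skew.** On an assumed 1–5 score, the step from 1 to 2 becomes ln 2 = 0.693 and the step from 4 to 5 becomes ln(5/4) = 0.223, so the lower step counts about 3.1 times as much. The simulations below use 10,000 trials per shape, 34 per arm, correlated items (six scored 1–5 or three scored 1–4), an effect of about 0.60 SD, and Welch tests on both scales:

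| Assumed shape | Control skew, raw → log | Power raw | Power logged | Mann-Whitney |
|---|---|---|---|---|
| Six-item, mild ceiling | −1.33 → −2.06 | 69.1% | 66.1% | 72.3% |
| Six-item, strong ceiling | −1.99 → −2.83 | 72.1% | 68.9% | 76.6% |
| Three-item, mild ceiling | −1.19 → −1.94 | 67.8% | 64.6% | 68.1% |
| Three-item, strong ceiling | −1.63 → −2.46 | 70.1% | 67.4% | 71.4% |
| Six-item, symmetric (inter-item correlation 0.5) | −0.03 → −0.76 | 67.1% | 65.6% | 65.1% |
| Six-item, symmetric (correlation 0.6) | 0.00 → −0.77 | 67.4% | 65.7% | 65.4% |
| Three-item, symmetric | 0.00 → −0.68 | 67.8% | 65.9% | 65.9% |

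The log costs 2.7 to 3.2 points of power in the ceiling shapes and 1.5 to 1.9 in the symmetric ones. In the two Beta cases at N = 68 the mean residual skew went from −0.51 to −1.26 and from −0.85 to −1.45, and 97–99% of logged data sets still failed the normality check.

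**Type I error.** For the six-item symmetric shape with correlation 0.6, 20,000 trials gave 5.07% raw, 5.10% logged and 5.12% under the triggered rule. The ceiling shapes gave 4.1% to 4.5% under the triggered rule (3,000 trials).

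**Standardised effect.** In the ceiling shapes it falls from 0.596–0.597 to 0.558–0.564. With n per arm = 2(1.96 + 0.8416)² / d² for 80% power, that is 45 raw against 50–51 logged. In the Beta cases it hardly moves: 0.41 against 0.41, and 0.55 against 0.54.

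**Zeros.** If past-year ED visits were Poisson, the share of zeros would be exp(−0.5) = 61% at mean 0.5 and exp(−3) = 5% at mean 3. An offset c must then be invented. The weight of the step from 0 to 1 visit relative to 4 to 5 is [ln(1 + c) − ln c] / [ln(5 + c) − ln(4 + c)]: 11.0 for c = 0.1, 5.5 for c = 0.5, 3.8 for c = 1.

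**The case against.** The best reply is that little goes wrong in practice. The power cost is about 3 points, the tests keep their size, and if Goal 3 means a standardised effect size the rule barely touches it; no document says that the effect must be in points. Raw and logged tests disagreed on significance in only about 3% to 7% of trials in the continuous-score simulations at N = 68. The SAP adds that "sample size estimates will only be relevant should be given approval to continue". The item scoring, ceiling effects and correlations are assumptions, and the SAP refers the survey items to an appendix that is not available here. The deeper gap is that no primary outcome analysis is set out; writing one would settle the scale as well. All of this stands, and it limits severity. It does not make the rule sound: an analyst who used judgement instead would be departing from the written plan.

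Some stronger readings are tempting but unsupported:

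- A reader might infer that a data-triggered transformation inflates false positives. The simulations put the error at about 5%.
- A reader who tries several score shapes will see the ratio for one standardised effect vary and might blame the log. The same effect in points also varied, from 0.22 to 0.47 over six similar shapes, because the assumed SDs and control levels differ.
- A reader might carry the zero problem over to Goal 3. The variables that can plainly be zero are past-year ED visits, the Charlson index and the PHQ-9, which are descriptive or, at most, covariates in an adjustment that the SAP makes contingent on imbalance.
- The yes/no revisit outcomes cannot sensibly be logged, so correcting this rule needs no new effect measure for them.

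**Conclusion.** The point holds, and its severity is minor. As written, the rule covers outcomes and makes the effect measure for a scored outcome depend on the data and on an unstated criterion. That part rests on the text alone. The rest is conditional. If scores are left-skewed, the log deepens the skew, costs about 3 points of power at 34 per arm and lowers a standardised effect from about 0.60 to about 0.56; this assumes 1:1 allocation, a 0.6 SD effect and the item structures shown. Left skew itself cannot be confirmed, because neither the primary outcomes nor the score ranges are stated.

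A reader might conclude that Goal 3 cannot be met under this rule. That goes too far: a ratio can be converted to points if the control level is reported, and a log-scale effect can still size a later study. Goals 1, 2 and 4 are unaffected.

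**What to change.** Replace the log-transformation sentence in the SAP with:

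> Scored survey outcomes will be analysed in original units as the mean difference between arms with 95% CI (Welch t-test, or a linear model with robust standard errors if adjusted), whatever their observed distribution; a rank-based test will be a sensitivity analysis. Log transformation will be limited to strictly positive non-outcome variables named before outcome data are examined; covariates that can be zero will be entered untransformed.

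The essential part is that each outcome's scale is fixed in advance and that logging is confined to named variables; the particular test and standard error are reasonable choices, not the only ones. The cost is a few SAP sentences and one extra sensitivity analysis per scored outcome. It needs no new data or patients, and no sample-size figure changes.
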